Monthly Follow-ups: For the 6 months following completion of the treatment phase, participants will be contacted three times (2-, 4-, and 6-months post-participation), via telephone or in person, to complete brief standardized measures of alcohol and substance use, as well as craving to assess for changes in these variables over the preceding 30 days. These brief contacts will be 15-20 min and tracking sobriety is the primary outcome measure of this study.

Procedure Risks

All procedures will be performed by staff trained specifically for the tasks for which they are responsible. All procedures, including the rTMS, and are considered low-risk procedures. rTMS is regarded as safe and without lasting side effects when established guidelines are followed. The primary serious adverse event associated with transcranial magnetic stimulation procedures are seizures, however, the estimated prevalence is very low at < 1%. In the case of transcranial magnetic stimulation-seizures, all have occurred during stimulation, there was no recurrence of seizures, and no incidences of status epilepticus. There have been no significant adverse cognitive, brain structural, neurologic or cardiovascular sequelae reported as a result of rTMS. Seizure risk will be minimized by careful patient selection by rigorously screening and exclusion of participants with history of seizure disorders or other conditions and medication use that increases risks of seizure. A seizure protocol is in place to avoid participant injury in the unlikely event that a seizure does occur attached.

The study will use the 3T UHP system at CNI. The UHP shares a common software and hardware architecture to GE's FDA-approved Premier system but uses a higher-performance gradient coil and is not FDA approved for diagnostic

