This study will not impose any restrictions on treatment/therapy after conclusion. At this point, the dMS treatment under investigation will only be available during the treatment phase of the study.

Study Endpoint(s)

In order to have sufficient power to evaluate the primary hypotheses of this study, it is expected to continue until all participants have completed the procedures and follow-up assessments.

BACKGROUND

Past Experimental and/or Clinical Findings

To date, TMS has emerged as a promising treatment avenue for AUD and is being tested in clinical trials with some encouraging results. The traditional target of the left dorsolateral prefrontal cortex (DLPFC) suggests that targeting the DLPFC alone may be insufficient, as treated individuals resume drinking shortly after treatment at similar rates as those receiving sham. One possible explanation is the well-documented atrophy of the PFC as a result of chronic heavy drinking. Therefore, targeting a structurally compromised brain region, may not yield the most robust effect. The literature describes how TMS treatment is associated with physiological changes in the brain at the treatment target area stimulated as well as in remote brain regions connected structurally or functionally. TMS has been associated with changes in long-term potentiation (LTP) or depression (LTD) to increase neuroplasticity through increases in brain-derived neurotrophic factor (BDNF) and is implicated in influencing the excitatory/inhibitory balance of GABAergic synapses. Given the demonstrated downstream impact, novel approaches for stimulation need to occur.

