rTMS administration: The rTMS operator will be fully trained and qualified to administer the procedure according to current safety practices and standards of care. Co-Is [name] and [name] have full rTMS training and, together with physician Co-Is also trained in rTMS, closely monitor the rTMS operator for adherence to safety protocols and rTMS administration for this proposal. Additionally, PI [name] will obtain full rTMS training and be available as an additional monitor and resource to the rTMS operator. The protocol employs all current established and standard rTMS treatment safety and monitoring for adverse events guidelines. The rTMS operator will monitor all participants for ear protection, coil placement, and seizure activity during all sessions.

All participants will be required to have abstained from alcohol or non-prescribed medication for 7 consecutive days prior to the first rTMS session. Prior to the first rTMS session, participants will be administered the CIWA- Ar and must score <8 (scores >8 are indicative of potential autonomic instability); participants with a score >8 will immediately be escorted to VAPAHCS ATS or further evaluation. Participants will be randomly screened x6 for alcohol (breath alcohol) and substance use (urine toxicology) prior to rTMS sessions during the 2-week treatment phase. If a participant tests positive or reports any alcohol or substance use during the 2-week rTMS treatment period, they will be immediately withdrawn from the study. Additionally, participants will be given the C-SSRS prior to each rTMS session to assess for current suicide risk. Although patients in the VAPAHCS are regularly screened for alcohol and substance use and suicide risk while in treatment, we will conduct random alcohol/substance screening and pre-rTMS session suicide risk assessment to ensure participant welfare.

Should a headache or site of stimulation discomfort occur, these symptoms usually readily respond to acetaminophen or ibuprofen. Any reported painfulness typically improves over time or completely remits. If dental pain

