occurs, study staff may be able to move the rTMS coil position or provide a bite block to reduce or eliminate this pain. To protect against possible hearing damage, participants will wear ear protection during rTMS sessions. This should greatly reduce the possibility of hearing loss. Hearing acuity testing pre-and-post rTMS is no longer a standard practice, given the remote likelihood of rTMS-related hearing loss.

Screening, Baseline and Treatment Phase: In the unlikely event that a seizure does occur, participants will be closely monitored and treated for any medical or psychological consequences. rTMS sessions will be conducted at the VAPAHCS MIRECC, which fully equipped to safely handle a seizure. If at any point during study participation, a participant has a seizure, the participant will be withdrawn from the study immediately although they will still be followed for protocol assessments. All seizures will be considered serious adverse events (SAE) and as such, will be reported to the study PI. We will immediately suspend enrollment if any of the participants experience a seizure during study participation and request that the Data Monitoring Safety Board (DMSB) evaluate the SAE data, to determine if enrollment of new participants should be resumed without protocol changes, if protocol modifications should be made before resuming enrollment, or if the study should be terminated. We recognize that study termination or modification based on SAEs, such as seizures, ultimately rests with the DMSB and the study PI. If a participant expresses suicidal ideation/intent and is determined to be a risk to self, a clinical evaluation will be immediately conducted by the PI (a licensed clinical psychologist), Co-Is (two licensed clinical psychologists and a board-certified psychiatrist), or by the participant's individual mental health provider, and/or a mental health emergency clinician. The participant will remain with qualified study personnel or a MIRECC clinician until the evaluation has been completed and a decision made about disposition in conjunction with the Chief of Mental Health Outpatient Clinic or the emergency mental health clinician.

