An Unanticipated Adverse Device Effect UADE is defined as any serious adverse effect on health or safety or any life-threatening problem or death caused by, or associated with, a device, if that effect, problem, or death was not previously identified in nature, severity, or degree of incidence in the investigational plan or application, or any other unanticipated serious problem associated with a device that relates to the rights, safety or welfare of participants. For this study an UADE is considered a category of SAE, which will be reported on the same form.

Collection and Recording: For this study, all SAEs and UADEs will be recorded on the SAE form, regardless of cause. The PI will be asked to determine whether the serious adverse event is related to:

- rTMS device
- rTMS treatment
- Medications used to treat AUD and/or co-occurring conditions

Collecting and recording SAEs/UADEs will begin at randomization and will continue throughout the follow-up phase. For a participant who ends study participation prior to the study's completion date, unresolved SAEs will be monitored and reported for 30 days after the End of Study date for that participant. In addition, the investigator must collect all SAEs reported to them for a period of 30 days after the study's completion.

Expedited Reporting of Serious Adverse Events SAEs and Unanticipated Adverse Device Effects UADEs: Study personnel will be responsible for initially evaluating all serious adverse events for participant safety concerns and will confer with the PI as required during this evaluation process. After being reviewed by the PI, any event deemed to be related, serious and unexpected will be reported to study investigators.

Expedited Reporting by the Sponsor to the FDA: PI will review the SAE report to assess completeness of documentation and to determine whether the SAE requires expedited reporting to the FDA. Specifically, if an event meets the criteria for unexpectedness (i.e., not previously reported and seriousness) it will be reported as required by regulation to the FDA within 10 working days for UADEs and within 7 calendar days for unexpected SAEs. Safety Reports of the sponsor receiving the report as required by regulation.

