Data Monitoring Safety Board (DMSB): Reporting of Adverse Events, Adverse Device Effects, Serious Adverse Events, and Unanticipated Adverse Device Effects. Study Personnel will generate tabulations of AEs and SAEs and present a summary of these to the DMSB on a schedule set by the DMSB. The DMSB will also determine when they should be unblinded to treatment assignment for the reviewing of adverse event data. The DMSB will advise the PI concerning whether the study should continue or be stopped for safety reasons.

Communication among the Investigative Team: The PI will have a weekly group lab meeting with all RAs. Additionally, the VAPAHCS MIRECC has weekly PI meetings to discuss issues relevant to ongoing MIRECC research projects. All key VA Co-Is associated with this project attend these weekly meetings.

Study Conclusion

The experiment will end at either the normal termination or whenever the subject decides to withdraw from the study. Participants will be asked to complete the brief monthly in-person or telephone assessments as described in the follow-up phase. In the event that an interim analysis demonstrates futility, the PI, or Co-Is will determine unacceptable level of risk, regulatory agencies mandate discontinuation of the study, or a product recall occurs that necessitates stopping the study, any planned rTMS treatments will be immediately discontinued.

e. Data Safety Monitoring Plan (DSMC)

i. Data and/or events subject to review

ii. Although this study protocol is low risk, and will enroll a modest number of participants, we will create a DSMB as we believe this is consistent with best clinical practices. Types of data and events that will be reviewed are: 1) Aggregate Data Analysis Reports; 2) Progress toward Study endpoints; 3)AEs, SAEs and unanticipated problems; 4) Protocol deviations. Person(s) responsible for Data and Safety Monitoring

The Protocol Director will be the only monitoring entity for this study.

iii. Frequency of DSMB meetings-N/A

iv. Specific triggers or stopping rules

In order to have sufficient power to evaluate the primary hypotheses of this study, it is expected to continue until all participants have completed the procedures and follow-up assessments.

v. DSMB Reporting

All SAEs will be reported within 24 hours of learning of the SAE.

Unanticipated problems involving risks to participants or others will be reported within 5 days.

vi. Will the Protocol Director be the only monitoring entity?

YES

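### Participants withdrawn for alcohol or substance use during treatment are not clearly kept in the 2-, 4- and 6-month follow-up, although those withdrawn for a seizure are

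*Protocol*

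**What the plan says.** Two withdrawal rules stand close together in the Protocol, RISKS, Procedures to Minimize Risk.

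- **Use during treatment** (rTMS administration). If someone "tests positive or reports any alcohol or substance use during the 2-week rTMS treatment period, they will be immediately withdrawn from the study". Six random breath and urine screens, plus self-report, serve to detect such use. The text says nothing about later assessments.
- **Seizure** (Screening, Baseline and Treatment Phase). Here "the participant will be withdrawn from the study immediately although they will still be followed for protocol assessments".

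Four other places bear on the point.

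- **Study Conclusion:** "The experiment will end at either the normal termination or whenever the subject decides to withdraw from the study". The next sentence reads: "Participants will be asked to complete the brief monthly in-person or telephone assessments as described in the follow-up phase".
- **Study Endpoint(s):** of the study as a whole, "it is expected to continue until all participants have completed the procedures and follow-up assessments".
- **Collection and Recording (SAEs and UADEs):** "For a participant who ends study participation prior to the study's completion date, unresolved SAEs will be monitored and reported for 30 days" after that person's end of study.
- **Monthly Follow-ups (detailed section):** "For the 6 months following completion of the treatment phase, participants will be contacted three times", at 2, 4 and 6 months. The same sentence also dates them from the end of participation, and Planned Duration of the Study dates them from the end of the study. Sobriety tracked at these contacts is named as the primary outcome.

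**The concern.** The authors separated withdrawal from loss of follow-up in the seizure rule but not in the rule for use. A coordinator who reads both could reasonably conclude that follow-up ends for someone withdrawn for use.

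The reason for removal is closely related to the primary outcome, so any loss is likely to be informative. The Follow-up Phase paragraph sharpens the contrast. A person who relapses after treatment is encouraged to return to addiction services, and no withdrawal is mentioned. The same drinking a few days earlier, during treatment, may end data collection.

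Whom to contact and when is a matter of data collection. An analysis plan can set a rule for missing outcomes, but it cannot supply contacts that were never made.

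**Working it through.** The protocol gives no figure to reproduce on this point, so the check is first textual and then a bound.

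**Does any sentence keep these participants in follow-up?**

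- Study Conclusion asks participants for the follow-up contacts. The sentence before it covers only normal termination and the subject's own decision to leave, not removal by the study.
- Study Endpoint(s) expects everyone to complete follow-up, which points towards keeping them, but does not mention people withdrawn.
- The 30-day provision for early leavers concerns unresolved SAEs only, and it ends before the first outcome contact at 2 months.

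The text therefore neither keeps nor expressly excludes them.

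**Is there a start date for their contacts?** The detailed follow-up section counts from completion of treatment, which a person withdrawn during treatment never reaches. On the two looser wordings, the clock might start at withdrawal. No date is fixed.

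**How much could be lost?** Inputs: N = 10 in one arm (Planned Enrollment) and 3 contacts each, so 3 × 10 = 30 planned contacts. Let k be the number not contacted and s the number sober at month 6 among those contacted. With no rule assumed for the denominator, the rate for all 10 lies in [s/10, (s + k)/10], a width of k/10.

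| k | Contacts lost | Undetermined part of the month-6 rate |
|---|---|---|
| 1 | 3 of 30 | 10 points |
| 2 | 6 of 30 | 20 points |
| 3 | 9 of 30 | 30 points |

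Illustration with s = 4 (an assumption). The exact (Clopper-Pearson) 95% intervals are 12.2% to 73.8% for 4/10, 18.7% to 81.3% for 5/10 and 26.2% to 87.8% for 6/10. The last column runs from the lowest lower limit to the highest upper limit over the possible true counts.

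| k | Possible rate for all 10 | 95% limits allowing for the missing outcomes |
|---|---|---|
| 0 | 40% | 12% to 74% |
| 1 | 40% to 50% | 12% to 81% |
| 2 | 40% to 60% | 12% to 88% |

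**Which way would the estimate move?** Take s = 4 and k = 1. Dropping the person gives 4/9 = 44.4%, which is too high if the true rate is 4/10 and too low if it is 5/10. Counting the person as not sober gives 4/10 = 40%, which is right in the first case and too low in the second. The direction depends on a rule that this document does not state.

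**How likely is at least one such withdrawal?** No rate is given. If each participant had a chance q of use during treatment, independently, the probability is 1 − (1 − q)^10. This is 40% for q = 5%, 65% for q = 10% and 89% for q = 20%. These values of q are assumptions.

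**The case against.** The strongest reply is that the general text leans towards retention. The request for follow-up contacts comes directly after a sentence on withdrawal and is not limited to completers. Study Endpoint(s) speaks of all participants. The seizure rule shows that in this document withdrawal can go together with continued assessment. This stands as far as it goes: a loss of data is possible, not established. It does not close the gap, because none of these sentences mentions removal for use, and the express exception for seizure can equally be read as excluding other cases.

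The number affected may also be zero. Participants live in a residential programme with 24-hour monitoring, have been abstinent for at least 7 days, and are screened regularly. This is fair, and no rate can be claimed.

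Alcohol use seen at withdrawal already settles sustained abstinence for that person, which is the protocol's stated goal. This is also true. It does not settle the preceding-30-day use and craving that the contacts measure, and use of another substance does not settle alcohol sobriety at all. The protocol does not name a month-6 30-day rate as an endpoint; it serves here as a natural summary of what the contacts record.

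Finally, with 10 participants imprecision dominates. The interval is already 12% to 74% with complete data, and one missing person raises only the upper limit, to 81%. With one arm there is no between-group comparison to bias. This limits the importance of the point but does not remove it.

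**Conclusion.** The concern holds in the form stated: these participants are not clearly kept in follow-up, and no start date for their contacts is fixed. If the rule for use is applied as written, primary-outcome data are lost for people removed because of an event tied to that outcome. Each such person leaves 10 points of the month-6 rate undetermined. The number affected and the size and direction of any bias are unknown; the figures for s = 4 and for the chance of withdrawal are illustrations. The consequence is confined to the sobriety estimate of a single-arm pilot, but the protocol means to use its results as preliminary data for a larger grant. The repair is cheap and the data cannot be recovered later, so it should be made.

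**What to change.** Leave the rule on stimulation as it is. Reconcile the rule for use (rTMS administration), the seizure rule and Study Conclusion by stating that participants withdrawn for use are still asked to complete the 2-, 4- and 6-month contacts. State the date from which those contacts are counted for someone who does not complete treatment, and use the same wording in Monthly Follow-ups and in Planned Duration of the Study.

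The cost is a short amendment, with matching consent wording if the consent form (not seen here) does not already cover it. Each affected person needs three contacts. The protocol gives their length as 10–15, 15 or 15–20 minutes in different places, so the total is 3 × 10 = 30 to 3 × 20 = 60 minutes, plus the follow-up payment of up to $50. Both are within what is budgeted for a participant who completes the study. The reported sobriety rate may be less favourable.

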An emerging advancement is the use of coils that target deeper regions of the brain and have the potential of targeting multiple, interacting brain networks. The coil configuration in this technique (and proposed in this study) stimulates a broader area (volume of stimulation is 40.3 cm^3), as well as a deeper area (subdural depth is 3cm). Through the use of this less commonly used coil type (H7), we hypothesize that we will be able to modify core nodes within the salience network that are otherwise not reached through traditional figure-of-eight coil approaches. Notably, there are only two published studies to date that utilize these H-coils for AUD, and only one focusing on the H7 coil proposed in this study. Harel and colleagues (2022) recently reported that an H7 stimulation protocol similar to the one proposed here resulted in changes in functional connectivity AND lower heavy drinking days in the active condition compared to the sham condition. However, it remains unclear if the proposed stimulation strategies will have an objectively measurable impact on their respective brain targets.

The proposed project will begin to explore if deep TMS treatments will be associated with 1) changes in task-based activation to emotional stimuli and 2)

whether these changes are associated with a reduced risk of relapse after standard VA treatment.

We believe this proposed work will provide preliminary data for a larger grant submission that could allow for a more complex study design to fully answer gaps in current knowledge about deep TMS H7 coil as a possible treatment approach for AUD.

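### Participants withdrawn for alcohol or substance use during treatment are not clearly kept in the 2-, 4- and 6-month contacts that measure the primary outcome

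*Protocol*

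**What the plan says.** Four parts of the protocol bear on this.

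- **Substance-use rule** (Procedures to Minimize Risk, rTMS administration): breath alcohol and urine toxicology are checked at random six times during the two treatment weeks. When someone "tests positive or reports any alcohol or substance use during the 2-week rTMS treatment period, they will be immediately withdrawn from the study". Nothing is said about later assessments.
- **Seizure rule** (same section, Screening, Baseline and Treatment Phase): after a seizure, "the participant will be withdrawn from the study immediately although they will still be followed for protocol assessments".
- **Follow-up and primary outcome** (Monthly Follow-ups, in the detailed design section): "For the 6 months following completion of the treatment phase, participants will be contacted three times", at 2, 4 and 6 months post-participation, by telephone or in person. The contacts record alcohol and substance use "as well as craving to assess for changes in these variables over the preceding 30 days", and "tracking sobriety is the primary outcome measure of this study".
- **General statements**: Study Conclusion says "Participants will be asked to complete the brief monthly in-person or telephone assessments as described in the follow-up phase". Study Endpoint(s) says of the study that "it is expected to continue until all participants have completed the procedures and follow-up assessments".

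The design is a single arm of 10 Veterans in a 28-day residential program.

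**The concern.** Stopping stimulation after alcohol or drug use is a reasonable safety step and is not in question. The difficulty is that the rule ends participation in the study and is silent on follow-up, whereas the seizure rule shows that the authors could separate the two when they chose to.

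If the silence is read as ending contact, the primary outcome is missing for people selected by an event closely related to that outcome. Such missingness is likely to be informative. With one arm and 10 people, no comparison group or larger sample offsets it. A statistical analysis plan can decide how to count these people, but it cannot recover contacts that were never made. Counting them as not sober would replace a measurement with an assumption.

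The sobriety result is meant to inform a larger grant. So is the second question in Past Experimental and/or Clinical Findings, about brain changes and "whether these changes are associated with a reduced risk of relapse after standard VA treatment".

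**Working it through.** The protocol gives no figure to reproduce here: no rate of use during treatment and no target for sobriety. The check is first textual, then illustrative.

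**1. Does the text keep these participants in follow-up?**

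- *Suggesting no:* withdrawal is from the study. The clause that retains assessments appears in the seizure rule only. The six months run from completion of the treatment phase, which a person stopped mid-course does not reach. For someone who ends participation early, the section on serious adverse events provides only for 30 days of monitoring of unresolved events.
- *Suggesting yes:* the same Monthly Follow-ups sentence also times the contacts post-participation, a date that a stopped participant does have. Study Conclusion and Study Endpoint(s) speak of participants generally and make no exception. The seizure rule shows that, in this protocol, withdrawal from the study can coexist with continued assessment.
- *Result:* neither reading is settled.

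**2. Is use during treatment the same event as the outcome?** Each contact asks about the preceding 30 days. The earliest, at 2 months, looks back over roughly the second month, so use during the two treatment weeks falls outside every window. The Objectives section speaks of a major relapse period, which a single lapse need not be. The trigger is therefore related to the outcome but not identical to it.

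**3. How many might be removed?** The rate p is unknown. For assumed values, with 10 participants:

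| Assumed p | none: (1 − p)^10 | at least 1 | at least 3 |
|---|---|---|---|
| 5% | 60% | 40% | 1.2% |
| 10% | 35% | 65% | 7.0% |
| 20% | 11% | 89% | 32% |

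**4. What could it do to the result?** Assume that 4 of 10 are truly sober. This borrows the complement of the 60% relapse figure in Objectives. That figure concerns major relapse and is stated as a minimum, so 40% is an illustration, not an estimate. Let k be the number removed and not contacted.

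| k | Observed, if none of those removed would be sober: 4/(10 − k) | Observed, if all of those removed would be sober: (4 − k)/(10 − k) | Removed counted as not sober, if all were sober: (4 − k)/10 | Range for all 10, if 4 of those followed are sober: 4/10 to (4 + k)/10 |
|---|---|---|---|---|
| 0 | 40% | 40% | 40% | 40% |
| 1 | 44% | 33% | 30% | 40% to 50% |
| 2 | 50% | 25% | 20% | 40% to 60% |
| 3 | 57% | 14% | 10% | 40% to 70% |

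If those removed are sober at the average rate, 40% is expected throughout. If none of them would be sober, counting them as not sober recovers 4/10 = 40%.

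**5. Against sampling error.** Exact (Clopper-Pearson) 95% intervals are 12% to 74% for 4/10 and 16% to 84% for 4/8. Every observed value above, from 14% to 57%, lies inside the first interval.

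**The case against.** The strongest reply is that the protocol does not drop these people. Study Conclusion names two ways in which the experiment ends for a participant, normal termination or the participant's own decision. Removal for substance use is neither, and the next sentence says that participants will be asked for the follow-up assessments. Together with the post-participation timing and the expectation that all participants complete follow-up, this makes continued contact a fair reading. That stands: a reader might infer from the substance-use rule that these participants are excluded from follow-up, and the document does not say so. But the general sentences do not mention withdrawal imposed for use, and the specific rule lacks the clause that its neighbour has. Staff applying it literally could stop the contacts.

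A second reply is that the harm is conditional and small. Participants are abstinent for at least 7 days before treatment, live in a residential program and have 24-hour monitoring, so removals may be few or none. Three or more would be unlikely at assumed rates of 5% or 10%. This also stands, and it limits the point to a cheap improvement.

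A third reply is that if use during treatment counts as failure, the outcome is already known and an analysis plan can score it. A reader might indeed treat the trigger as failure on the primary outcome and conclude that sobriety must be overstated. The protocol does not support that: the 30-day windows exclude the treatment weeks, and later sobriety is unknown unless someone asks.

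**Conclusion.** The point holds as an ambiguity that should be removed. The substance-use rule withdraws people from the study without keeping them in assessments, and the rest of the protocol does not settle whether they are still contacted.

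If they are not, the primary outcome is unmeasured for people removed for a reason closely related to it. Inflated sobriety is the likelier result but not a certain one. In the illustration, 40% becomes 44%, 50% or 57% for one, two or three removals if none of those removed would have been sober. It falls to 33%, 25% or 14% if all would have been. These figures rest on an assumed 4 of 10 sober and assumed numbers of removals, and the shifts lie within the sampling error of a 10-person study. The firmer loss is that sobriety among all 10 would be known only within a range k/10 wide, and follow-up contact would close that gap.

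**What to change.** Amend the substance-use rule so that a positive test or a report of use stops dTMS immediately, and add the seizure rule's clause that the participant is still followed for protocol assessments. State that this means at least the 2-, 4- and 6-month contacts, timed from the scheduled last treatment day so that stopped participants have the same windows as the rest. Record the use during treatment. How these participants are counted can be left to the analysis plan.

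Cost per stopped participant: 3 contacts × 15 to 20 minutes = 45 to 60 minutes, and up to $50. For three such people this is at most 3 hours and $150. The contacts are already planned for every participant. Some who leave the program may be harder to reach, but telephone contact is allowed.

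The post-treatment visit with MRI may be offered but is optional. It adds 4 hours and $75 each, so the total is 4 h 45 min to 5 h and up to $125 per person. Without it, the change protects the sobriety outcome only; the analysis linking brain change to relapse still lacks these participants.
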